9.7. Data analysis

The proportions and drug utilization patterns comparisons of 11 study drugs will use all the patients satisfying inclusion and exclusion criteria (raw data). Adherence, persistence, discontinuation, recurrence, and adverse outcomes comparison of 11 study drugs will use both raw data and matched data where patients will be matched on demographic and clinical characteristics. All outcome variables will be summarized *descriptively* through the tabular and graphical display of mean values, medians, ranges and standard deviations of continuous variables of interest and frequency distributions of categorical variables. Safety outcomes of treatments will be estimated from time-to-event models. The 95% confidence intervals for the estimates will be calculated and $p < 0.05$ will be considered significant. All analyses will be carried out using SAS version 9.4 which is installed on HIRA server. Analysis and reporting will be compliant with Strengthening the Reporting of Observational Studies in Epidemiology (STROBE) recommendations.

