Patient demographics and provider characteristics	Covariates	HIRA Database	
The following patient demographics and provider characteristics will be defined using medical claims
 
 - Age - Gender - Region of provider - Specialty of provider - Class of clinic/hospital
Number of visits	Covariates	HIRA Database	
The number of provider visits will be calculated from medical claims
 
 - Inpatients visits - Outpatient visits - Emergency room visits

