7 STATISTICAL METHODOLOGY AND STATISTICAL ANALYSES

7.1 STATISTICAL METHODS

Means, medians, and standard deviations will be provided for continuous variables when performing descriptive analysis of continuous data. Numbers and percentages will be provided for dichotomous and polychotomous variables when performing descriptive analysis of categorical data. Bivariate comparisons of baseline characteristics and outcomes measures will be provided. Appropriate tests (e.g., t-test, chi-square test) will be used based on the distribution of the measure. The cumulative incidence rate for clinical outcomes (major bleeding event, and stroke) will be calculated. The incidence rate will be calculated as the number of patients who experience the event divided by the observed time at risk. An unadjusted Kaplan Meier curve will be drawn to illustrate time-to-event.

PFIZER CONFIDENTIAL

[figure not shown]
The propensity score matching (PSM) technique and the propensity score weighting technique will be used to control for confounders when comparing the antidepressants. After PSM, no significant differences are expected among all pre-index measures between the antidepressant cohorts except for clinical indication differences. Also covariates in Table 3 will be included in multivariate logistic regression framework for each antidepressant choice (binary variable of 1 for choice and 0 for no choice). Covariates will include variables such as age, geographic region, CCI score, and comorbidities. Non-pharmacologic treatments will be used as a covariate if dependent variable is adherence, persistence, or discontinuation since a previous study reported accompanying number of non-pharmacologic treatments significantly increase adherence of antidepressants (Ahn J et al., 2011). The final lists of variables to be used in the model will be discussed and determined during analysis development, after reviewing the pre-matched descriptive tables and post-matched pre-index measures. All data analysis will be executed using statistical software SAS version 9.4 or later.

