7.2 STATISTICAL ANALYSES

7.2.1 Study Drug Analysis in Acute Phase

- To understand the top 11 antidepressants usage among the Korean patients with depression in acute treatment phase
- Primary analysis
- Endpoints:
 - Proportion of 11 antidepressants, by age (<20, 21-64, > 65), by gender, by age and gender
 - Choice of index drug
 - Initial doses used, average daily doses of each antidepressant
 - The average length of treatment with index medication before therapy change occurs (switching, combination, augmentation, discontinuation)
 - Adherence measured by medication possession ratio and persistence during first 90 days and 180 days of treatment period, respectively
- Population: patients who meet inclusion criteria and exclusion criteria in section 4.1 and classified by the index antidepressant out of 11 top antidepressants in the Korean market (Table 2)
- Significance on continuous variables will be tested by ANOVA (if equal variance condition satisfied) or the Kruskal-Wallis H test (otherwise). Provider specialty and other patient characteristics will be used to fit antidepressant choice by multivariate logistic regression analysis of each study drug choice.
- Covariates: antidepressant class covariates such as SSRIs, SNRIs, and other ADs will be used as grouping variables.
- Missing values will be dropped from the analysis
- The role of this analysis is to provide information on study antidepressants in the acute phase of drug therapy for Korean patients with depression.

PFIZER CONFIDENTIAL

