7.2.5 Selection of Antidepressant by Specialty Analysis

- To understand the antidepressant choice among the Korean providers by specialty
- Secondary analysis
- Endpoints:
 - Proportion of 11 antidepressants by provider specialty
- Population: patients who satisfies the acute treatment phase population and with a prespecified comorbidity
- Significance on continuous variables will be tested by ANOVA (if equal variance condition satisfied) or Kruskal-Wallis H test (otherwise). Provider specialty and other patient characteristics will be used to fit antidepressant choice by multivariate logistic regression analysis of each study drug choice.
- Covariates: antidepressant class covariates such as SSRIs, SNRIs, other ADs will be used as grouping variables. Provider specialty and other patient characteristics will be used to fit antidepressant choice by multivariate logistic regression analysis of each study drug choice.
- Missing values will be dropped from the analysis.
- The role of this analysis is to provide information on antidepressant selection in the acute phase of drug therapy for Korean patients with depression and comorbidity by each comorbidity group.

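### The drug-choice logistic models use provider-level predictors but make no allowance for correlated prescribing within a provider, so intervals for those predictors can be too narrow

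*SAP*

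**What the plan says.** SAP 7.1 sets up one binary model per drug: "Also covariates in Table 3 will be included in multivariate logistic regression framework for each antidepressant choice". The provider rows of Table 3 (SAP 5.4) list "Region of provider", "Specialty of provider" and "Class of clinic/hospital". Section 7.1 names region again: "Covariates will include variables such as age, geographic region, CCI score, and comorbidities".

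Section 7.2.1 then states: "Provider specialty and other patient characteristics will be used to fit antidepressant choice by multivariate logistic regression analysis of each study drug choice". The sentence recurs in 7.2.2 and 7.2.3 and appears twice in 7.2.5. It groups specialty with the characteristics of the patient. The endpoint of 7.2.5, which serves secondary objective 3, is "Proportion of 11 antidepressants by provider specialty".

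On inference, protocol 9.7 says "The 95% confidence intervals for the estimates will be calculated and $p < 0.05$ will be considered significant". That sentence follows one on safety models; I read it as covering the estimates of the whole section. SAP section 3 lists no hypotheses or decision rules.

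Neither document mentions clustering, a provider identifier, random effects, GEE or robust variance. SAP 7.1 leaves the final list of model variables open, but says nothing about the variance.

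**The concern.** The outcome is a decision made by the prescriber. Prescribers and institutions have habits, so two patients of the same provider are likely to be more alike in drug choice than two patients of different providers. Region and class take one value per institution, and specialty takes one value per prescriber. For such predictors the information lies largely in the number of providers, while ordinary logistic regression counts every patient as a separate observation.

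At stake is the reported precision of the specialty, region and class coefficients. The model appears in both primary analyses (7.2.1, 7.2.2) and two secondary ones (7.2.3, 7.2.5). With eleven drugs and a long list of specialties there are many contrasts in which a chance difference between groups of providers could be reported as a finding.

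**Working it through.** **Inputs from the documents.** Significance level 0.05 with 95% intervals (protocol 9.7; two-sided assumed). Binary logistic model per drug (SAP 7.1). There is no planned figure to reproduce, because neither document gives an ICC, a number of providers or a number of patients per provider. With independent patients the nominal 5% holds exactly.

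**Assumed inputs.** Patients per provider (m) from 3 to 100; ICC of drug choice from 0.01 to 0.20.

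**Formulas, for a predictor constant within the provider and equal provider sizes.**
- Design effect: DEFF = 1 + (m − 1) × ICC
- Factor by which the interval should be wider: √DEFF
- Actual type I error of the unadjusted test: 2 × [1 − Φ(1.96/√DEFF)]

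Example, m = 20 and ICC 0.05: DEFF = 1 + 19 × 0.05 = 1.95; √1.95 = 1.40; 2 × [1 − Φ(1.96/1.40)] = 16.0%.

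| m | ICC (observed scale) | DEFF | Width factor | Type I error |
|---|---|---|---|---|
| 3 | 0.01 | 1.02 | 1.01 | 5.2% |
| 5 | 0.01 | 1.04 | 1.02 | 5.5% |
| 5 | 0.05 | 1.20 | 1.10 | 7.4% |
| 10 | 0.05 | 1.45 | 1.20 | 10.4% |
| 20 | 0.05 | 1.95 | 1.40 | 16.0% |
| 50 | 0.05 | 3.45 | 1.86 | 29.1% |
| 50 | 0.10 | 5.90 | 2.43 | 42.0% |
| 100 | 0.10 | 10.90 | 3.30 | 55.3% |

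**Check by simulation, no true effect.** With 1,000 providers and a 10% drug share, the unadjusted test rejected in 10.0% (m = 10, ICC 0.05), 15.5% (m = 20, ICC 0.05) and 41.8% (m = 50, ICC 0.10), in line with the table. With unequal provider sizes the same settings gave 16.3%, 31.1% and 59.3%. Cluster-robust errors gave 4.2% to 7.3% across all settings run.

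**ICC on the latent (logit) scale.** With 1,000 providers, 20% of them in the specialty of interest and a 20% drug share, the ratio of robust to unadjusted standard error is about 1.23 at m = 20, latent ICC 0.05, and about 3.5 to 3.6 at m = 100, latent ICC 0.20. A ratio of 3.61 implies 2 × [1 − Φ(1.96/3.61)] = 59%. At m = 3 to 5 with ICC 0.01 to 0.05 the ratio is 1.00 to 1.05. A given latent ICC corresponds to a smaller observed-scale ICC, which is why the two scales give different rates at the same nominal value.

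**Where the effect does not appear.** A patient-level covariate unrelated to provider kept 4.7% and 4.5%. If specialty varies at random within an institution and the habit sits only at institution level, the standard-error ratio is 1.00 and rejection stays at 4% to 6%, even with 100 patients per institution and latent ICC 0.20.

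**The case against.** The strongest reply has four parts.

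*Specialty need not be constant within an institution.* Table 3 lists specialty apart from class of clinic or hospital, and several specialties named under secondary objective 3 can share one hospital. This stands. A reader might infer that the error for specialty always runs towards false positives. That follows only if the cluster has one specialty, or if habits sit at department or prescriber level, and the documents describe no such structure. Robust errors clustered on the institution stay valid in either case.

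*The size is assumed.* This stands too. A reader who starts from 20 or more patients per provider and a latent ICC of at least 0.05 would put the floor at about 11%. The documents do not exclude few patients per provider, particularly outside psychiatry, where the inflation is negligible.

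*The study is exploratory.* SAP section 3 has no hypotheses, the endpoint of 7.2.5 is a descriptive share, and region and class are only covariates. In a national cohort, small differences may reach p < 0.05 even with correct errors. This lowers the stakes but does not make the intervals valid. A large cohort is no cure, since the factor depends on m and ICC and grows with m.

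*Independence is inferred from silence.* True. But a plan that names logistic regression and no variance method points to the default model-based errors. A reader might also infer that chi-square tests of share by specialty are prescribed. They are not: SAP 7.1 gives that test only as an example, and 7.2.5 names none for shares.

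**Conclusion.** The concern holds for predictors that are constant within a provider: region, class, and specialty under the conditions given above. Followed as written, with default errors, the plan gives intervals that are too narrow for these whenever drug choice is positively correlated within a provider. The false-positive rate at nominal 5% lies between about 5-8% and about 55-60% over the assumed range, and nothing in the documents places the study within it. For specialty varying within hospitals, the size may be nil and depends on the clustering structure.

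A reader might go further and take this as undermining the study's conclusions on drug choice. The documents do not support that: there is no confirmatory test, and the estimated shares and odds ratios are unaffected. What is affected is their stated precision. The change is worth making, but it is not critical.

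**What to change.** Where the extract holds an institution identifier, fit the drug-choice models in SAP 7.2.1, 7.2.2, 7.2.3 and 7.2.5 with the institution as the cluster, using GEE with an independence working correlation or survey logistic regression with a cluster statement, both in SAS 9.4. Report cluster-robust 95% intervals and p-values, and use the same variance for any test of drug share by specialty. Add the identifier to Table 3 and describe specialty as a provider characteristic. Reporting the number of institutions and the ICC would let readers judge the size.

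If the identifier is not available, state that intervals for provider-level predictors ignore clustering, and interpret them descriptively without p-values.

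Cost: about one statement per model, and wider intervals. Point estimates do not change under either method. The condition on the identifier matters: Table 3 does not list one, protocol 9.6 routes data through a request and release committee, and SAP section 1 records that the amendment was made during data analysis and cites limited data capacity. A missing identifier could therefore need a new request, in which case the descriptive fallback applies.

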7.2.2 Study Drug Analysis in Maintenance Phase

- To understand the top 11 antidepressants usage among the Korean patients with depression in maintenance treatment phase
- Primary analysis
- Endpoints:
 - Choice of study drug
 - Average length of new treatment maintenance
 - Average number of co-medications (e.g., atypical antipsychotics, mood stabilizer, thyroid hormone, psychostimulant) when following changes occur from initial monotherapy: switching, combination, augmentation
 - Medication compliance (adherence, discontinuation, and persistence)
 - Recurrence by each antidepressant, by compliance
 - Risk of adverse events
- Population: patients from the acute treatment phase who started maintenance treatment (after 90 days from the index date)
- Significance on continuous variables will be tested by ANOVA (if equal variance condition satisfied) or Kruskal-Wallis H test (otherwise). Provider specialty and other patient characteristics will be used to fit antidepressant choice by multivariate logistic regression analysis of each study drug choice.
- Covariates: antidepressant class covariates such as SSRIs, SNRIs, and other ADs will be used as grouping variables.
- Missing values will be dropped from the analysis
- The role of this analysis is to provide information on study antidepressants in the maintenance phase of drug therapy for Korean patients with depression.

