2.2 STUDY OBJECTIVES

Primary objectives:

1. Explore baseline characteristics and drug utilization patterns of 11 commonly used antidepressant therapy during 90 days of acute treatment phase
 - Top 11 commonly used antidepressants according to local market data are as follows:
 - Escitalopram, paroxetine, fluoxetine, mirtazapine, duloxetine, sertraline, venlafaxine, tianeptine, vortioxetine, desvenlafaxine, bupropion
 - Proportion of antidepressants prescribed by sex, age (<20, 21-64, > 65), sex and age combined
 - Initial doses used, average daily doses of each antidepressants
 - Average length of treatment with index medication before therapy change occurs (switching, combination, augmentation, discontinuation)
 - Adherence and persistence measured by medication possession ratio during first 90 days of treatment period
2. Explore drug utilization patterns such as therapy changes, medication compliance and recurrence relationship, and risk of adverse outcomes during maintenance phase
 - The choice of antidepressant, average length of new treatment maintenance, average number of co-administered medications (e.g., atypical antipsychotics, mood stabilizer, thyroid hormone, psychostimulant) when following changes occur from initial monotherapy:
 - Switching
 - Combination
 - Augmentation
 - Medication compliance and recurrence
 - Compliance measured as adherence and persistence
 - Recurrence
 - Relationship between recurrence and compliance

PFIZER CONFIDENTIAL

- *Risk of adverse outcomes measurement between individual ADs that are well known to be treatment-related (e.g., hyponatremia, GI bleeding, fractures, falls, risk of intracranial hemorrhage, attempted suicide/self-harm, myocardial infarction, epilepsy/seizures, stroke/transient ischemic stroke)*

Secondary objectives:

1. *Choice of antidepressants and drug utilization patterns in patients with various comorbidities*
 - *Psychiatric comorbidities*
 - *Mild cognitive impairment (MCI)*
2. *The relationship of non-pharmacologic treatment and discontinuation, medication compliance*
 - *Non-pharmacologic treatments may include: cognitive behavioral therapy (CBT), frequency of physician visit during acute and maintenance phase of treatment*
 - *Frequency of visit during the first 3 months of acute phase and its relationship to treatment maintenance at 4, 5, 6, 7, 8, 9 month time points and discontinuation rate*
3. *Choice of antidepressants by non-psychiatric specialty*

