5.1 EFFICACY/EFFECTIVENESS ENDPOINT(S)

Medication compliance (persistence, discontinuation, adherence) along with recurrence are main primary efficacy endpoints and they are defined as follows:

1. MPR (medication possession ratio)
For each of 11 study drugs, the MPR will be calculated by (Days of medication possession from the prescriptions filled in the 180 days) / (180 days + extra days of drug supply from the last prescription fill during the 180 days)
2. Persistence
For each of 11 study drugs, the average length of treatment on the index drug during the first 180 day period (allowing 14 day permissible gap) will be

PFIZER CONFIDENTIAL

calculated. Switching, combination, augmentation, discontinuation will terminate the persistent period.

3. Discontinuation

For each of 11 study drugs chosen as index drug, the percentage of discontinuation in the first 90 days from the index date (acute treatment phase) will be measured (allowing 14 day permissible gap)

4. Adherence

For each of 11 study drugs chosen as index drug, adherence will be measured by MPR and persistence during the first 90 day and 180 day from the index date, respectively (acute treatment phase). MPR ≥ 0.75 and persistence ≥ 90 will be considered as adherence.

* For those period with any identified adverse outcome such as GI bleeding will be considered as a non-adherent period.

5. Recurrence

Recurrence during the acute treatment phase was operationally defined as either one of the following being satisfied:

- 1) Inpatient episode with a diagnosis code in Table 1
- 2) Inpatient episodes via the department of psychiatry or emergency medicine
- 3) Inpatient episode via nursing hospital
- 4) Emergency room visit with a diagnosis code in Table 1
- 5) Suicide attempt identified by the following KCD-7 codes:
 - T40 Poisoning by narcotics and psychodysleptics [hallucinogens]
 - T41 Poisoning by anaesthetics and therapeutic gases
 - T42 Poisoning by antiepileptic, sedative-hypnotic and antiparkinsonism drugs
 - T43 Poisoning by psychotropic drugs, not elsewhere classified
 - T54 Toxic effect of corrosive substances
 - T60 Toxic effect of pesticides
 - X60-X84 intentional self harm
- 6) Augmentation of the following non-AD drugs
 - Antipsychotic: amisulpride, aripiprazole, olanzapine, quetiapine, risperidone, perphenazine
 - Anticonvulsant: carbamazepine, valproic acid, lamotrigine
 - Mood stabilizer: lithium
 - Anxiolytic: buspirone
 - Thyroid hormone: levothyroxine, liothyronine

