Persistence	Primary outcome	HIRA Database	
For each of 11 study drugs, the average length of treatment on the index drug during the first 180 day period (allowing 14 day permissible gap) will be calculated
 
Switching, combination, augmentation, discontinuation will terminate the persistent period

Discontinuation	Primary outcome	HIRA Database	For each of 11 study drugs chosen as index drug, the percentage of discontinuation in the first 90 days from the index date (acute treatment phase) will be measured (allowing 14 day permissible gap)
Adherence	Primary outcome	HIRA Database	
For each of 11 study drugs chosen as index drug, adherence will be measured by MPR and persistence during the first 90 day and 180 day period from the index date, respectively (acute treatment phase). MPR ≥ 0.75 and persistence ≥ 90 will be considered as adherence.
 
* For those period with any identified adverse outcome such as GI bleeding will be considered as non-adherent period

Drug utilization pattern in acute phase	Secondary outcome	HIRA Database	
During the first 90 day period starting from the index date, the following types of drug utilization pattern is recorded
 
- monotherapy (kept on the index medication)- switching (switched to other antidepressant)- combination (adding other antidepressant)- augmentation (adding other non-AD drug such as antipsychotic)
Drug utilization pattern in maintenance phase	Secondary outcome	HIRA Database	
During the second 90 day period (91 ~ 180 days) starting from the index date, the following types of drug utilization pattern is recorded
 
- choice of antidepressant- monotherapy (kept on the same medication)- switching (switched to other antidepressant)- combination (adding other antidepressant)- augmentation (adding other non-AD drug such as antipsychotic)

PFIZER CONFIDENTIAL

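### The average length of new treatment is compared between drugs with no observation window counted from the therapy change and no censoring; the distortion is large if observation stops at day 180 and small if it runs to the data end.

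*SAP*

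**What the plan says.** Primary objective 2 (SAP 2.2) asks for "The choice of antidepressant, average length of new treatment maintenance, average number of co-administered medications" after switching, combination or augmentation from initial monotherapy. SAP 7.2.2, labelled a primary analysis, repeats the endpoint as "Average length of new treatment maintenance". Its population is "patients from the acute treatment phase who started maintenance treatment (after 90 days from the index date"), with no upper limit in days. The method given is "Significance on continuous variables will be tested by ANOVA" if variances are equal, and Kruskal-Wallis otherwise. Protocol 9.7 adds: "The 95% confidence intervals for the estimates will be calculated and $p < 0.05$ will be considered significant".

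Table 3 of the SAP has no row for this endpoint. The nearest definitions are counted from the index date:

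- Persistence is "the average length of treatment on the index drug during the first 180 day period (allowing 14 day permissible gap"), and so concerns the index drug only.
- The maintenance utilization pattern is recorded "During the second 90 day period (91 ~ 180 days) starting from the index date".

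The Kaplan-Meier sentence in SAP 7.1 follows the incidence of clinical outcomes and is not assigned to treatment length. Protocol 9.7 reserves time-to-event models for safety outcomes.

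**The concern.** A new treatment begins on the day of the change, and that day varies between patients. A window counted from the index date therefore gives late changers less time to show how long they stay on the new drug. ANOVA and Kruskal-Wallis take a length that was cut off while treatment was still running as if it were a completed treatment. Two drugs that patients keep equally long could then show different means only because one tends to be introduced later. With p < 0.05 declared significant, such an artefact could be reported as a difference between drugs. Propensity matching or weighting on pre-index measures does not correct it, because the day of change comes after index.

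**Working it through.** The plan states no expected duration, power or sample size for this endpoint, so it has no figure to reproduce.

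**Inputs from the documents.** Index dates run from 1 Jan 2018 to 30 Jun 2019, and the data end on 31 Dec 2020 (SAP 2.1). The maintenance phase is days 91-180 from index (SAP Table 3).

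**Assumptions, not in the documents.** True length on the new drug is exponential with mean m = 120 days (range 60-240), the same for every drug. Change days are uniform over the stated range. For the data-end reading, index dates are uniform over the intake period.

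**Formulas.** With F days of observation after the change, the expected observed length is m(1 - exp(-F/m)) and the share cut off is exp(-F/m). Both are averaged over the change days.

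**Reading A: observation stops at day 180, so F = 180 - t.** A change on day 100 leaves 80 days and one on day 170 leaves 10.

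| True mean m | Observed mean, changes on days 91-180 | Share cut off | Mean over a common 180 days |
|---|---|---|---|
| 60 | 29 | 52% | 57 |
| 120 | 35 | 71% | 93 |
| 240 | 39 | 83-84% | 127 |

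- The common-window value for m = 120 is 120 × (1 - exp(-180/120)) = 120 × 0.777 = 93 days.
- If changes are spread over days 1-180 instead, m = 120 gives an observed mean of 58 days with 52% cut off.
- By change-day band (m = 120), the observed means are 55 days for days 91-120, 37 for days 120-150 and 14 for days 150-180, although true persistence is identical.
- The effect on the test was simulated for two drugs with identical persistence, with an assumed 500 patients per drug and 400 replicates, counting the day of change as observed. With change days on 91-170 for one drug and 101-180 for the other, Kruskal-Wallis rejected in 93% to 100% of replicates over m = 60 to 240. With the same change-day distribution for both drugs it rejected in 4% to 5.5%.

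**Reading B: observation runs to 31 Dec 2020.** Follow-up from index is 550 days (index 30 Jun 2019) to 1,095 days (index 1 Jan 2018).

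| True mean m | Share cut off | Observed means by the same three bands |
|---|---|---|
| 60 | about 0% | 60.0, 60.0, 60.0 |
| 120 | 0.7% | 119.4, 119.2, 118.9 |
| 240 | 7% | 225, 223, 221 |

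The spread between bands is 119.4 - 118.9 = 0.5 day for m = 120 and 225 - 221 = 4 days for m = 240. For the least-observed patients (index 30 Jun 2019), changes on day 91 and day 150 differ by 0.1, 1.6 and 9.8 days for m = 60, 120 and 240.

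**Fixed window from the change.** With 180 days for everyone, the expected mean no longer depends on the change day (57, 93 and 127 days). The latest case is 30 Jun 2019 + 180 + 180 days = 24 Jun 2020, before the data end.

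**The case against.** The strongest reply is that the SAP never applies a day-180 stop to this endpoint. The row for days 91-180 says when the type of utilization pattern is recorded, not how long a new treatment is followed. The population in 7.2.2 has no upper bound. Secondary objective 2 looks at treatment maintenance up to month 9, and the extract runs to the end of 2020. The protocol's amendment table refers to a follow-up period in Figure 1 that was extended to what was then the data end; the figure could not be read in the text reviewed, so its content cannot be called missing. All of this stands, and under that reading the distortion is small.

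A reader might infer that the planned analysis will make later-introduced drugs look as if they are kept for less time, with most lengths cut off. The documents do not support that. It needs the day-180 stop, and it needs drugs to differ in their typical change day, which neither document reports. The 71% figure also confines changes to days 91-180, while changes from initial monotherapy are recorded in the first 90 days too.

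The stakes are also moderate: the objectives are exploratory, SAP section 3 marks hypotheses and decision rules as not applicable, and Table 3 labels the maintenance utilization pattern a secondary outcome. None of this supplies the missing rule. The endpoint sits in a primary analysis with significance tests, and the text leaves open a choice between a large distortion and a small one.

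**Conclusion.** The point holds as a gap in definition with a conditional bias. SAP 7.2.2 compares a plain mean with no observation window anchored at the change and no censoring. Under the day-180 reading and exponential lengths with mean 120 days, it would report about 35 days (58 if changes fall anywhere in days 1-180) against 93 over a common window. Under follow-up to 31 Dec 2020, the difference between change-day bands is under 1 day for a mean of 120 and about 4 days for a mean of 240. The exponential form, the means and the spread of change days are assumptions. A false difference between drugs arises only if their change days differ. The SAP was amended during data analysis, so the rule should be fixed in writing and not left to programming.

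**What to change.** In SAP 7.2.2, and as a row in Table 3, define new-treatment length as days from the date of the switch, combination or augmentation, with the 14-day permissible gap already used for persistence, over a fixed 180 days after the change for every patient. State which change days count. The window is complete within the data for any change up to day 180, and for the latest index date up to day 550 - 180 = 370.

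With the window complete, the planned mean and Kruskal-Wallis test are adequate. Use Kaplan-Meier and the restricted mean to 180 days only where death or loss of data cuts the window short.

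The cost is a short SAP edit and one variable re-derived from data already in the extract. The downside is that lengths beyond 180 days are truncated, so the result should be labelled as mean time on the new treatment within 180 days.
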